8.2.9. Population PK Analysis or PK/PD Modeling (excluding the Continuation Cohort)

PK and PD data from this study may be analyzed using compartmental or mixed-effect modeling approaches and may also be pooled with other study results. PK/PD modeling may be attempted to investigate any causal relationship between PF-04449913 exposure and biomarkers or significant safety endpoints. The results of these analyses, if performed, may be reported separately.

8.2.10. Other Analyses

8.2.10.1. Standard Analyses

8.2.10.1.1. Study Conduct and Subject Disposition

An accounting of the study subjects will be tabulated. Subjects not completing the treatment/study (completing the treatment means the subject completes treatment for 12 cycles; completing the study means the subject completes the post-treatment follow-up period) will be listed along with the reason for discontinuation.

Analysis set: Screened patients.

Table produced by: dose level and cohort.

Table:

Subject disposition and evaluability will be summarized. Summary table will include following number of subjects:

- Assigned to study treatment (treated, completed, discontinued);
- Analyzed for DLT;
- Analyzed for safety (AEs, laboratory data);
- Analyzed for PK (PK parameter, PK concentration);
- Analyzed for PD;
- Analyzed for QTc.

Listings: Subject disposition and evaluability will be listed.

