23. Follow-up Visit: At least 28 days, and no more than 35 days following discontinuation of treatment (up to 42 days after the last dose of study drug if treatment was stopped for prolonged myelosuppression) patients require review of concomitant medications and assessment for resolution of any treatment related toxicity. Patients continuing to experience toxicity at this point following discontinuation of treatment will continue to be followed at least every 4 weeks until resolution or determination, in the clinical judgment of the Investigator, that no further improvement is expected.

Table 4. Combination Cohort 2: PF-04449913 + Cytarabine/Daunorubicin in Fit Patients with AML or High-Risk MDS

Protocol Activity	Screening	Induction					Consolidation				Maintenance	End of Ttx/ Withdrawal	Post-Ttx Follow-Up ²⁴
		Lead-in (first cycle only)	Up to 2 Induction Cycles (28-day cycle)				2-4 Consolidation Cycles (28-day cycle) ^{***}				Maximum of 6 Maintenance Cycles (28-day cycle)		
	Within 28 Days Prior to Study Entry	Day -3 *	Day 1	Day 3	Day 10 (±1 days)	Day 21 (±2 days)	Day 1	Day 5	Day 10 (±1 days)	Day 21 (±2 days)	Day 1 (±2 days)		
Baseline documentation													
Informed Consent ¹	X												
Medical/Oncologic History ²	X												
ECOG Performance Status ³	X	X	X				X				X	X	
Safety Labs/Measurements													
Vital Signs (BP and pulse) **	X	X	X				X				X	X	
Physical Examination ^{4**}	X	X	X		X	X	X	X		X	X	X	
CBC (Complete blood count) with differential ^{5 **}	X	X	X	X	X	X	X	X	X	X	X	X	
Blood Chemistry ^{6 **}	X	X	X	X	X	X	X	X	X	X	X	X	
Urinalysis with micro ^{7 **}	X	X	X				X				X	X	
PT/PTT (or aPTT)/INR ^{**}	X	X	X				X				X	X	
Pregnancy test ⁸	X	X					X				X	X	
Triplicate 12-lead ECG ⁹	X	X			X		X				X	X	
ECHO or MUGA scan ²¹	X												
Other Clinical Assessments													
Adverse Event (AE) ¹⁰		X	X	X	X	X	X	X	X	X	X	X	X
Prior/Concomitant Medications and Treatments ¹¹	X	X	X	X	X	X	X	X	X	X	X	X	X
Recording of red blood cell and platelet transfusions ²²	X	X	X	X	X	X	X	X	X	X	X	X	
Drug Compliance ¹²		X	X	X	X	X	X	X	X	X	X	X	

	Screening	Induction					Consolidation				Maintenance			
		Lead-in (first cycle only)	Up to 2 Induction Cycles (28-day cycle)				2-4 Consolidation Cycles (28-day cycle)***				Maximum of 6 Maintenance Cycles (28-day cycle)			

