A total of 15 patients will be treated in this cohort and DMR rate will be evaluated. Treatment with PF-04449913 in combination with LDAC may continue until disease progression or relapse, patient refusal, or unacceptable toxicity occurs (whichever is first). All patients will be followed for survival every 8 weeks up to 2 years from the first dose of the last patient enrolled in the study, or until death, end of the study, or patient withdrawal of consent, whichever comes first, regardless of initiation of new cancer therapy (follow-up on survival status will no longer be required after Protocol Amendment 8).

Combination Cohort 2 (Fit Patients):

In this cohort, patients defined as “fit for intensive chemotherapy” based on pre-defined criteria (See Inclusion Criteria) will receive PF-04449913 once daily continuously in combination with daunorubicin and cytarabine during induction and consolidation. For the first induction cycle only, PF-04449913 will commence on Day -3 and will then be given once daily continuously for the duration of treatment. Following completion of induction and consolidation, single-agent PF-04449913 may be given to eligible patients as maintenance therapy for a maximum of 6 cycles.

A total of 6 patients will be treated in this cohort and followed up for DLT evaluation. If ≤ 1 of the 6 patients experiences a DLT event by the end of Induction Cycle 1, the tolerability of the combination will be confirmed. If 2 or more of the 6 patients experience a DLT by the end of Induction Cycle 1, additional lower dose levels may be tested using identical criteria to those outlined above with respect to DLT events.

Treatment will continue until disease progression or relapse, patient refusal, or unacceptable toxicity (whichever is first). Fit patients who complete induction, consolidation and 6 cycles of maintenance with PF-04449913 will be deemed to have completed the study treatment. However, patients who complete the 6 cycles of maintenance and demonstrate clinical benefit with manageable toxicity, and are willing to continue receiving single-agent PF-04449913, may be given the opportunity to do so following agreement between the Investigator and Sponsor, and pending study drug availability. If treatment continues beyond 6 cycles of maintenance, study procedures should continue to be performed as listed in [Table 4](#) (Schedule of Activities).

Combination Cohort 3 (Azacitidine Combination):

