5.3.4.3. Maintenance

[figure not shown]
Patients are eligible for maintenance therapy if they have:

- Completed the induction phase;
- Completed at least 2, but not more than 4 cycles of consolidation;
- Maintained a CR/CRi through the end of consolidation;

- Maintenance begins at the end of consolidation (following Day 28 of the last consolidation cycle) and consists of PF-04449913 administered orally once daily continuously in the morning as monotherapy in 28-day cycles. Maintenance will continue for a maximum of six cycles after the completion of consolidation; thereafter, all patients will discontinue treatment (unless demonstrating clinical benefit and upon agreement between the Investigator and Sponsor).

Patients unable to maintain their CR/CRi while on maintenance may still be eligible to continue on maintenance therapy based on investigator Input and Sponsor approval. If a patient demonstrates unequivocal disease progression or unacceptable toxicity, they must be discontinued from treatment and followed as described in Section [5.3.7](#).

Figure 5. Treatment Flow Diagram for Combination Cohort 2 (Fit Patients)

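### The SAP's single 12-cycle definition of treatment completion does not fit Combination Cohort 2, the Expansion Cohort or Combination Cohort 3, so their disposition counts would be wrong

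*SAP*

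**What the plan says.** SAP 8.2.10.1.1 (Study Conduct and Subject Disposition) gives one definition of completing treatment: "completing the treatment means the subject completes treatment for 12 cycles". No cohort is named. The disposition table is specified as "Table produced by: dose level and cohort", and its first row is "Assigned to study treatment (treated, completed, discontinued"). Patients who do not complete the treatment or the study "will be listed along with the reason for discontinuation".

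The protocol's study design section sets the length of treatment cohort by cohort:

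- **Monotherapy Cohort and Combination Cohort 1** (Protocol 3.1.1, 3.1.2): up to 12 cycles, with continuation possible by agreement.
- **Combination Cohort 2** (Protocol 3.1.2, repeated in SAP 2.1): "Fit patients who complete induction, consolidation and 6 cycles of maintenance with PF-04449913 will be deemed to have completed the study treatment".
- **Expansion Cohort** (Protocol 3.1.2, repeated in SAP 2.1): "Treatment with PF-04449913 in combination with LDAC may continue until disease progression or relapse, patient refusal, or unacceptable toxicity occurs". There is no cycle limit.
- **Combination Cohort 3** (Protocol 3.1.2, 5.3.1.2): at least six cycles are intended, then treatment goes on with no upper limit.
- **Continuation Cohort** (Protocol 3.1.3): one patient, no cycle limit.

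**The concern.** A definition that suits two cohorts is applied to all of them, and it errs in opposite directions. In Combination Cohort 2 it is too strict: a patient can finish everything the protocol asks for and still be reported as not completing, with a reason for discontinuation demanded when there was none. In the Expansion Cohort and Combination Cohort 3 it creates a completion point that the protocol does not have: a patient who passes cycle 12 counts as completed whatever ends treatment later.

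Disposition is a standard table, and readers use it to judge tolerability. Here a Combination Cohort 2 count would understate how many patients finished the planned course, while an Expansion Cohort or Combination Cohort 3 count would report completions of a course that has no end.

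**Working it through.** **Combination Cohort 2.** Inputs:

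- Induction, from Protocol Table 4: "Up to 2 Induction Cycles (28-day cycle"), so 1 or 2 cycles.
- Consolidation, from Protocol 5.3.4.3: "Completed at least 2, but not more than 4 cycles of consolidation", so 2, 3 or 4 cycles.
- Maintenance: 6 cycles for protocol completion (Protocol 3.1.2).

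Total cycles = induction + consolidation + maintenance, counted across the three phases and compared with 12:

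| Induction | Consolidation | Maintenance | Total | Complete under protocol | Complete under SAP 8.2.10.1.1 | Extra maintenance cycles needed to reach 12 |
|---|---|---|---|---|---|---|
| 1 | 2 | 6 | 9 | yes | no | 3 |
| 1 | 3 | 6 | 10 | yes | no | 2 |
| 1 | 4 | 6 | 11 | yes | no | 1 |
| 2 | 2 | 6 | 10 | yes | no | 2 |
| 2 | 3 | 6 | 11 | yes | no | 1 |
| 2 | 4 | 6 | 12 | yes | yes | 0 |

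Five of six patterns fail the SAP rule, including every pattern with a single induction cycle. Under the protocol's rule all six count as complete.

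**Expansion Cohort and Combination Cohort 3.** No cycle total can be computed, because the protocol gives no planned end. Twelve cycles take 12 × 28 = 336 days, or 336 / 30.4 ≈ 11 months. From then on the SAP label is fixed as completed, even if the patient later stops for toxicity or progression.

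The primary analysis shows a further effect in the Expansion Cohort. SAP 3 places it after the 15th patient's Cycle 9/Day 1 assessment, about 19 months after the first patient's first dose. At that visit the 15th patient has had 8 × 28 = 224 days of cycles and cannot have completed 12. A patient enrolled early could have. If both are still on treatment, one is completed and the other is not, and the table row offers no ongoing category.

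**Number of patients in reach.** Combination Cohort 2, Expansion Cohort and Combination Cohort 3: 6 + 15 + 6 = 27 of 49 planned. This is the size of the affected cohorts, not a count of misclassified patients.

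**The case against.** The strongest reply is that nothing is lost. SAP 8.2.10.1.2 requires its own summary and listing of discontinuations on the safety analysis set, with no 12-cycle condition. SAP 8.2.4.1 tabulates discontinuations due to adverse events, again with no cycle limit. SAP 8.2.10.1.4 reports treatment duration and cycles started. This stands. A reader might infer from SAP 8.2.10.1.1 that late stops for toxicity disappear from the report; the documents do not support that. What remains is that one patient can be completed in one output and discontinued in another.

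A second reply is that the SAP already carries the right Combination Cohort 2 rule in section 2.1, so a sensible programmer would use it. That makes the point an inconsistency within the SAP as well as with the protocol, but does not resolve it: the section that specifies the table is the one with the 12-cycle rule. How the CRF records completion is not in the documents.

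A third reply concerns size. Few Expansion Cohort or Combination Cohort 3 patients may reach cycle 12. The protocol cites median overall survival of 8.3 to 8.8 months for the LDAC combination (1.2.8.1.3) and 10.4 months for azacitidine alone (1.2.4.3). If those medians applied here, which is an assumption, fewer than half would be alive at about 11 months. This also stands, and it limits the number affected.

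**Conclusion.** The point holds as a reporting error of limited size. Followed literally, SAP 8.2.10.1.1 gives wrong completed and discontinued counts in three cohorts: Combination Cohort 2, for protocol-completers with fewer than 12 total cycles; and the Expansion Cohort and Combination Cohort 3, for patients who pass cycle 12.

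Stronger readings are not supported:

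- Not every Combination Cohort 2 completer is misclassified. The 2 + 4 + 6 course reaches 12, and maintenance extended by agreement can bring the others there.
- Five of six is a count of possible courses, not a patient frequency; the cohort has six patients.
- The Continuation Cohort does not add a fourth set of wrong counts. SAP 8.2 gives it listings only.
- No inference is touched. The DMR test, the DLT rules and the analysis sets do not use this definition.

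The conclusion assumes that Combination Cohort 2 cycles are totalled across the three phases (the SAP does not say) and that the definition is programmed as written.

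**What to change.** Replace the single definition in SAP 8.2.10.1.1 with one by cohort that follows the protocol:

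- Monotherapy Cohort and Combination Cohort 1: 12 cycles.
- Combination Cohort 2: induction, consolidation and six maintenance cycles, whatever the total.
- Expansion Cohort, Combination Cohort 3 and the Continuation Cohort listing: no completed-treatment category. Report each patient as ongoing or discontinued, with the reason.

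State also that the disposition table and the SAP 8.2.10.1.2 outputs use the same definition of discontinuation, so that the two agree. The cost is a few lines of SAP text and a cohort-specific derivation. No new assessments and no change to treatment rules are needed.

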8.2.10.1.2. Subject Discontinuation

Analysis set: Safety Analysis Set.

Table produced by: dose level and cohort. For the Continuation Cohort, only the listings will be produced.

Table: Subject discontinuation will be summarized.

Listing: Information of subject discontinuation will be listed.

8.2.10.1.3. Baseline Characteristics

Analysis set: Safety Analysis Set.

Table produced by: dose level and cohort. For the Continuation Cohort, only the listings will be produced.

Tables:

- Demography (sex, age, race, weight, height);
- Subject accrual (site No.);
- Primary diagnosis (diagnosis, duration);
- Medical history (past, present);
- ECOG performance status at Screening.

The duration of primary diagnosis is obtained by the time from the date of histopathological diagnosis to one of enrollment.

Listings:

All the above characteristics will be listed. In addition, following information will be also provided.

- Prognostic scores (Sokal Score for CML, IPSS for MDS, Dupriez Score for MF);
- Childbearing potential (childbearing potential, contraceptive method);
- Primary diagnosis as AML (AML-Fab subtype, AML disease history).

8.2.10.1.4. Treatment Administration

Analysis set: Safety Analysis Set.

Table produced by: dose level, cohort and regimen. (Regimen is for Combination Cohort 2, fit patients; induction, consolidation and maintenance) For the Continuation Cohort, only the listings will be produced.

Analysis: Initial planned dose is defined as prescribed dose at the start day defined below. The units of the prescribed daily dose of cytarabine and daunorubicin (Combination Cohort 2, fit patients), and azacitidine (Combination Cohort 3) are transformed mg/m² to mg based on body surface area (BSA) on Cycle 1 Day 1.

Definition of the start day for initial planned dose

- PF-04449913 in Combination Cohort 1: Cycle 1 Day 3;
- PF-04449913 on induction cycle in Combination Cohort 2: Cycle 1 Day -3;
- PF-04449913 in Combination Cohort 3: Cycle 1 Day 2;
- PF-04449913 for others, LDAC, daunorubicin, cytarabine and azacitidine: Cycle 1 Day 1.

Tables:

Dose administration will be summarized as follows:

- Treatment duration (day) by regimen. (Number (%) of subjects with duration category, median, range) [Duration category (day): ≤1, 2-7, 8-14, 15-28, 29-56, 57-84, 85-112, ≥113];
- Total number of cycle started (median, range);
- Number (%) of subjects started each cycle;

- Number (%) of subjects with at least one cycle delay, where cycle delay is defined as any delay of the cycle start date, based on the previous cycle's start date;
- Number (%) of subjects with at least one dose reduction, where dose reduction is defined as a day when the actual dose taken is less than the initial planned dose for any reason with the exception that a day with total dose administered of 0 mg is not considered a dose reduction [by study treatment]. In the event that the prescribed dose varies across cycles as a result of body weight change of >10% per protocol, the adjusted prescribed dose is considered the initial planned dose for the relevant cycles;
- Number (%) of subjects with at least one dose interruption/missed dose, where dose interruptions/missed dose is defined as a planned dosing day with 0 mg total dose administered only PF-04449913.

Relative dose intensity will be summarized using mean, standard deviation, median, and range as follows:

- Actual dose intensity [mg/week] = total dose received / (cycle length / 7), where
 - Total dose received [mg/cycle] is an actual total dose in the cycle,
 - Cycle length [day/cycle] = date of end of treatment in the cycle – date of start of treatment in the cycle + 1, that is the cycle length includes the delay until the next cycle.
- Relative dose intensity by cycle = {total dose received / (dose duration / 7)} / planned dose intensity, where
 - Dose duration [day/cycle] = sum of dose duration from each dosing record,
 - Planned dose intensity [mg/week] = (prescribed dose at start of cycle * planned dose duration per protocol) / (planned dose duration per protocol / 7).
- Overall relative dose intensity = {sum of “total dose received” / (sum of “dose duration” / 7)} / {sum of “prescribed dose at start of cycle * planned dose duration per protocol” / (sum of “planned dose duration per protocol” / 7)}.

Listings:

- Listings by subject: study drug, start date and stop date of each dosing period within each cycle (including records with 0 mg), prescribed dose and actual received dose for each period, any missed doses with unknown dates (Y/N), number of missed doses with unknown dates, reason for any dosing changes.
- Listings by study treatment, subject and each cycle: cycle start/stop date and study day, planned total dose (based on prescribed dose at Day 1 of each cycle), prescribed total dose, total dose received, percentage of starting dose (compared to Day 1 prescribed dose for that cycle), percent of prescribed dose (ie, compliance derived by

the following equation, total dose received/planned total dose), dose delay (yes/no), dose reduction (yes/no), dose interruption (yes/no).

- Listings of dose intensity by study treatment, prescribed dose at start of cycle, planned dose duration per protocol, total dose received, cycle length, dose duration, planned dose intensity, actual dose intensity, relative dose intensity by cycle.

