5.3. Administration

5.3.1. General Guidelines

In the monotherapy cohort, PF-04449913 administered as a single agent will be evaluated. In the combination cohort, three different PF-04449913 combinations (with LDAC for the unfit patient population, with cytarabine/daunorubicin for the fit patient population, and with azacitidine for the azacitidine patient population) will be evaluated. In the Continuation

Cohort, PF-04449913 continuously administered as a single agent will be evaluated for safety. Patients should be instructed to take their medication at approximately the same time each day and to not take more than the prescribed dose at any time.

Study drugs are administered in cycles. Bone marrow evaluations are performed at specified times to determine clinical response and treatment progression decisions within the trial (except for the Continuation Cohort).

5.3.1.1. In the combination cohorts, all patients should be weighed within 72 hours prior to dosing for every cycle to ensure they did not experience either a weight loss or gain >10% from the prior weight used to calculate the amount of cytarabine, daunorubicin required, or azacitidine for dose preparation. Decision to recalculate cytarabine, daunorubicin, or azacitidine dose based on the weight obtained at each cycle can be in accordance with institutional practice for changes in weight of 10% or less; however, if the patient experienced either a weight loss or gain of >10%, the amount of cytarabine, daunorubicin, or azacitidine required for study drug preparation and administration must be recalculated using this most recent weight obtained. Study Treatment Duration in the Monotherapy Cohort

Treatment with PF-04449913 may continue for up to 12 cycles or until disease progression or relapse, patient withdrawal, or unacceptable toxicity occurs (whichever comes first). However, patients who complete 12 cycles of study treatment demonstrating clinical benefit with manageable toxicity, and are willing to continue receiving the study treatment, may be given the opportunity to do so upon agreement between Investigator and Sponsor and pending study drug availability.

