- PF-04449913 will be administered in the morning at approximately the same time as the first LDAC subcutaneous injection on days these agents are dosed together. On days that PF-04449913 is dosed alone, PF-04449913 will be administered in the morning at approximately the same time each day;
- LDAC will be given at a dose of 20 mg (not adjusted for the patients weight) subcutaneously (SC) twice daily (morning and evening; approximately 12 hrs apart) on Days 1-10 days of the 28 day cycles.
- If the in-clinic study visits cannot be conducted due to COVID-19-related reasons, LDAC administration may be skipped only once. In such case, the safety assessments should be performed by phone or video contact, and/or by utilizing the test results from a local clinic if applicable. If 2 or more consecutive skips are required, the investigator and the Sponsor should have a consultation to determine the necessity of the study treatment discontinuation.

5.3.4. PF-04449913 in Combination with Cytarabine/Daunorubicin (Combination Cohort 2: Fit Patients)

In this cohort, treatment consists of 3 distinct phases: induction, consolidation and maintenance. All patients must meet specific criteria to enter each phase and will be required to wait the full 28 days of each cycle before progressing (Figure 4). The only exception is for receiving the second cycle of induction which, if needed, can occur as early as Day 21 of induction Cycle 1.

Patients may require placement of a central venous catheter prior to initiation of therapy per institutional guidelines.

Figure 4. Overview of Combination Cohort 2 (Fit Patients) Treatment Plan

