5.3.10. Recommended Dose Modifications [Combination Cohort 3 (Azacitidine Combination)]

Every effort should be made to administer the study drug treatment according to the planned dose and schedule. This section, package insert or institutional guideline for dose modification of azacitidine should be followed.

In the event of significant toxicity, dosing may be interrupted, delayed and/or reduced as outlined below. In the event of multiple toxicities, dose modification should be based on the worst toxicity observed. Patients must be instructed to notify investigators at the first occurrence of any adverse symptom/s.

Dose modifications may occur in three ways:

- **Within a cycle:** Dosing interruption until adequate recovery followed by dose reduction (if required) of PF-04449913 during a given treatment cycle. Azacitidine dosing interruption is not allowed within a cycle unless there is an unexpected or unacceptable study drug combination related toxicity or \geq Grade 3 non-hematologic toxicity.
- **Between cycles:** The next treatment cycle may be delayed if toxicity from the preceding cycle persists. If a treatment interruption continues beyond Day 28 of the current cycle for any agent, then the day when full treatment (all agents in the combination) is restarted will be counted as Day 1 of the next cycle for all agents.

- **In the next cycle:** Dose reduction may be required based on toxicities experienced in the previous cycle.

A study treatment related continuous treatment interruption or delay of >28 days (21 days in case of azacitidine related) for non-hematologic toxicity OR >42 days for prolonged myelosuppression defined as ANC <500/ μ L or platelet count <10 x10⁹/L in a normal bone marrow with <5% blasts and no evidence of disease or dysplasia, will result in permanent discontinuation from treatment, unless the patient is demonstrating clinical benefit as agreed by the Investigator and Sponsor (Table 18 and Table 19).

5.3.10.1. Dose Interruptions for Azacitidine and PF-04449913 [Combination Cohort 3 (Azacitidine Combination)]

Azacitidine

Azacitidine dose interruption is not allowed within a cycle unless there is an unacceptable or unexpected study drug combination related toxicity or \geq Grade 3 non-hematologic toxicity. In this case azacitidine dosing may be resumed following the dose modifications listed in Table 18 and Table 19.

After Cycle1, each dose of azacitidine will be allowed to be shifted by a plus or minus 3 day window.

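### The SAP's dose-reduction count exempts weight-based recalculation only above 10%, so a smaller recalculation permitted by the protocol is counted as a reduction at an unchanged mg/m² dose

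*SAP*

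**What the plan says.** SAP 8.2.10.1.4 (Treatment Administration) takes the initial planned dose as the dose prescribed on a stated start day, which is Cycle 1 Day 1 for LDAC, cytarabine, daunorubicin and azacitidine. Prescribed mg/m² doses of cytarabine, daunorubicin and azacitidine are converted to mg "based on body surface area (BSA) on Cycle 1 Day 1". A patient has a dose reduction on any non-zero dosing day that meets this definition: "where dose reduction is defined as a day when the actual dose taken is less than the initial planned dose for any reason".

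There is one exemption for weight: "In the event that the prescribed dose varies across cycles as a result of body weight change of >10% per protocol", the adjusted dose becomes the initial planned dose for the cycles concerned.

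Protocol 5.3.1 requires a weight before each cycle and makes recalculation of cytarabine, daunorubicin or azacitidine mandatory when weight has moved by more than 10%. Below that threshold recalculation is optional. It "can be in accordance with institutional practice for changes in weight of 10% or less".

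The same SAP section counts patients with at least one late cycle, "where cycle delay is defined as any delay of the cycle start date, based on the previous cycle's start date". The protocol schedules allow Day 1 of later cycles to fall within ±2 days (Tables 1 to 3, and maintenance in Table 4) or ±3 days (Table 5). In Combination Cohort 3, Protocol 5.3.10.1 adds that after Cycle 1 "each dose of azacitidine will be allowed to be shifted by a plus or minus 3 day window".

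**The concern.** The protocol allows two kinds of weight-based recalculation, and the SAP exempts only one. The exemption shows that its authors did not mean a weight adjustment to be read as a reduction in treatment. For changes of 10% or less, however, the reference stays at the Cycle 1 Day 1 mg figure. A patient still receiving the full protocol mg/m² dose can therefore enter the reduction count because of modest weight loss, and whether that happens depends on site habit. A patient with a larger loss does not enter it.

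In a cohort of 6, one such patient moves the reported percentage by 1/6, or about 17 points. A reader of the table could take that as poorer tolerance of the backbone.

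The delay count has a similar feature on a smaller scale: a start one day late, fully inside the visit window, is a delay.

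**Working it through.** The plan gives no figure to reproduce here, so the check sets the definitions side by side and follows one patient through them.

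**Inputs.** Azacitidine 75 mg/m²/day (Protocol 5.3.5); the reduction and exemption rules (SAP 8.2.10.1.4); optional recalculation at 10% or less and mandatory above (Protocol 5.3.1). Assumed: 160 cm and 60 kg at Cycle 1 Day 1, a site that recalculates at every cycle, and BSA = √(kg × cm / 3600), since the documents name no BSA formula.

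**Dose reduction.** Reference: √(60 × 160 / 3600) = 1.633 m²; × 75 = 122.5 mg.

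| Weight change | kg | BSA (m²) | Dose at 75 mg/m² | Reference | Counted as reduced? |
|---|---|---|---|---|---|
| −1% | 59.4 | 1.625 | 121.9 mg | 122.5 mg | Yes |
| −5% | 57.0 | 1.592 | 119.4 mg | 122.5 mg | Yes |
| −11% | 53.4 | 1.541 | 115.5 mg | reset to 115.5 mg | No |

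All three patients receive exactly 75 mg/m². The one with the largest fall in mg is the one not counted.

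**Which drugs.** PF-04449913 is not adjusted for body size (Protocol 5.3.2) and LDAC is a fixed 20 mg (Protocol 5.3.3), so neither can be affected. In Cohort 2 the answer depends on the reference:
- Read literally, the cytarabine reference is the induction dose of 100 mg/m²/day. Consolidation is 2 g/m²/day (Protocol 5.3.4.2), twenty times as much, so weight loss of 10% or less cannot bring it below the reference. Only a second induction cycle is exposed, and the same holds for daunorubicin, which is given in induction only.
- If each regimen has its own reference, as the by-regimen tables may imply, consolidation cycles are exposed too.

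**A tempting repair that fails.** Suppose reduction were judged in mg/m² using each cycle's BSA. Let the same patient gain 5%, to 63 kg, at a site that does not recalculate, as Protocol 5.3.1 allows. BSA = √(63 × 160 / 3600) = 1.673 m², and the unchanged 122.5 mg is 122.5 / 1.673 = 73.2 mg/m². That is below 75, so the patient would be counted although nothing was changed. The artefact moves from weight loss to weight gain.

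**Cycle delay.** With visits anchored to a calendar, two compliant starts can be 28 + 2 + 2 = 32 days apart (±2 window) or 28 + 3 + 3 = 34 days apart (±3 window). Any gap above 28 days counts. Because each start is compared with the previous one, an early start followed by a return to the calendar also counts. If a share q of later cycles starts late but in window, independently, P(at least one delay in k later cycles) = 1 − (1 − q)^k:

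| q (assumed) | k = 5 | k = 11 |
|---|---|---|
| 5% | 23% | 43% |
| 10% | 41% | 69% |
| 20% | 67% | 91% |

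No document gives q. The range shows only that the count may be sensitive to scheduling.

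**The case against.** The strongest answer is that this table is an all-cause exposure count by design, and that toxicity-driven changes are reported elsewhere. SAP 8.2.4.1 tabulates temporary discontinuations or dose reductions due to AEs, for any AE and for treatment-related AEs. The by-subject dosing listing gives the reason for each change, which is readable in cohorts of 6. Relative dose intensity uses the dose prescribed at the start of each cycle, so recalculation does not distort it. The section sits under Other Analyses, no decision rule uses it, and no exposure comparison between cohorts is planned. Nothing shows that any site recalculates at 10% or less.

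Most of this stands, and it sets the severity. It does not remove the inconsistency: a truly all-cause count would need no weight exemption, and the SAP has one that stops at 10%. The section 8.2.10.1.4 and 8.2.4.1 counts could also differ with no explanation in the tables.

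On delays, a start inside the window can fairly be read as on schedule, and the SAP sets no threshold in days. That makes it a request for clarification. Ignoring every in-window delay would also carry a cost, because it would hide short delays caused by toxicity.

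**Conclusion.** The gap is real, narrow and minor. At sites that recalculate for weight changes of 10% or less, a downward recalculation at an unchanged mg/m² dose counts as a reduction, while one after a larger loss does not. The planned cohort mainly affected is the 6 patients of Combination Cohort 3. In Cohort 2 it is limited to repeat induction, or extends to consolidation if the reference is set per regimen. The number of patients actually miscounted cannot be derived from the documents, since it depends on site practice and weight change.

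A reader might infer more, and the documents do not support it:
- That the tolerability findings are inflated. Tolerability is judged on DLTs, and the DLT and DMR analyses are untouched.
- That all 12 planned patients of Cohorts 2 and 3 are equally exposed. Cohort 2 exposure depends on the reading above.
- That any Day 1 shift is a delay. An early start is not one in itself, and Day 1 of induction and consolidation has no window in Table 4.
- That nearly every patient will show a delay. Assuming starts spread evenly over a ±2-day window, with 2 of 5 days late, gives 1 − 0.6^8 = 98% over 8 starts, but no document supports that spread.

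**What to change.** In SAP 8.2.10.1.4, extend the existing exemption. Whenever the prescribed mg dose changes because of a weight-based recalculation of any size that the protocol permits, the recalculated dose at the same mg/m² level becomes the initial planned dose for the relevant cycles. State also that a dose left unrecalculated after a weight change of 10% or less is not a reduction. This second sentence avoids the weight-gain artefact shown above. Say whether the Cohort 2 cytarabine reference is set once or separately for induction and consolidation.

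For cycle delay, keep the all-delay count, which retains short toxicity delays. Add a row for starts later than the protocol window allows: 2 days for Tables 1 to 3 and Cohort 2 maintenance, 3 days for Cohort 3. State whether lateness is measured from the previous actual start or from the calendar.

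The cost is SAP wording and derivation code. No protocol change is needed. Weight, dosing records and reasons for dosing changes are already planned to be collected.
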